3.9 Data Collection

Data will be collected at baseline, 1, 3, and 6 months. All data collection procedures will occur through remote means. Weights will be collected via e-scale, self-monitoring data will be collected objectively by the digital tools, health literacy will be assessed orally, and all other measures will be collected via web-based questionnaire (REDCap and a dietary recall tool⁴⁹). Fitabase software (Small Steps Lab, LLC) will be used to retrieve the objective self-monitoring data via Fitbit's API. At the time of each assessment, participants will be emailed instructions for weighing themselves on their e-scales, and sent a link to the web-based survey to complete measures. Reminders will be sent if weights are not reported or surveys not completed.

3.9.1 Masking

Participants will not be masked to treatment assignment, by design, as they will be informed before enrollment about the three types of self-monitoring to which they could be assigned. Study staff will not be masked to treatment assignment due to logistical limitations and the need for quality assurance. However, all surveys will be sent via REDCap and study staff will not have access to the allocation sequence. Once all data are collected, the study statistician ([name]) will analyze the primary outcome (weight change) in a masked fashion such that treatment assignment will not be revealed.

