3.4.2 Baseline Visit and Randomization

Individuals not randomized to receive the orientation session will receive an email invitation to sign up for a baseline visit. All participants will attend a baseline visit, regardless of orientation session assignment. At this baseline visit (~1-1.5 hours), trained study staff will confirm eligibility and describe study procedures. If individuals are interested in participating, study staff will obtain informed consent to assure that they fully understand the demands and purpose of the study before enrolling. Next, study staff will help participants create a Fitbit account and download the Fitbit app. Study staff will then administer a web-based dietary recall, an oral health literacy assessment, and a web-based baseline survey. Once the survey is completed, study staff will mail all participants an e-scale to obtain baseline weight measurement. Once the e-scale is delivered, participants will receive an email that provides information on syncing their e-scale with the Fitbit app, and will be prompted to weigh themselves the following morning using a standardized protocol. Within the week after the baseline visit, a 2nd unannounced web-based dietary recall will be administered, with reminders sent if it is not completed.

Once the weight assessment is completed, participants will be randomized to 1 of 8 experimental conditions via an algorithm on REDCap. Study staff will mail an activity

tracker (Fitbit Inspire 3) within 2 business days to those randomized to the conditions with self-monitoring of steps (i.e., conditions 3, 4, 7, 8; **Figure 2**, above). Once the tracker is delivered, participants will receive instructions for syncing the tracker with the Fitbit app. Study staff will be available to troubleshoot with device syncing, as needed. Then, the weight loss intervention will begin -- participants will receive an automated email describing their assigned intervention.

Following recommendations for factorial designs,³⁵ we will randomize participants to the 8 conditions using restricted randomization. We will stratify by sex assigned at birth and use permuted block randomization with a block size of 8. The allocation sequence was generated using SAS by the study's statistician ([name]) and stored in REDCap. Study staff will use REDCap to implement the random allocation sequence (i.e., randomize a participant) once both the baseline weight and web-based baseline surveys are submitted.

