Self-monitoring weight (Yes vs. No): Participants randomized to receive this component will be instructed to self-monitor their body weight daily via a Bluetooth enabled e-scale (the Fitbit Aria Air scale). These participants will receive a weekly weight loss goal of 0.5 to 2.0 lbs. (0.23 kg to 0.91 kg) per week, calculated as the magnitude of weight loss that is required to achieve 10% weight loss at 6 months. The e-scale will be synced with the Fitbit mobile app, providing graphical feedback.

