3.8.1 Primary Outcome

The primary outcome is weight change from baseline to 6 months (in kg), which will be assessed objectively via e-scale (Fitbit Aria Air) that will be mailed to participants. At each assessment, participants will receive an automated email in the morning instructing them to weigh themselves on the e-scale and follow best-practices⁴⁶: place the scale on a hard, flat surface; remove all articles of clothing and accessories; weigh on the scale in the morning before eating or drinking and after emptying their bladder; step on the scale and record the value; and repeat it 2 more times for a total of 3 weight measurements per time point. Weights will sync from the e-scale to the Fitbit app via Bluetooth; as a preventive measure in case of syncing errors, participants will also be asked to input their weight values on a web-based weight check-in form. There is high concordance between weights measured from commercial e-scales and those from scales used in a clinical setting.⁴⁷⁻⁴⁸

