Self-monitoring engagement will be assessed objectively for all 182 days (6 months) of the intervention using data collected from the Fitbit digital tools. Engagement will be operationalized as the percent of days in the intervention that participants self-monitor dietary intake, steps, and weight (each reported separately). For self-monitoring of diet, we will count days as valid if they have ≥ 800 kcal recorded, which is a common threshold. For self-monitoring of steps, we will count days as valid only if ≥ 1000 steps are recorded; this minimum threshold is used to minimize the possibility of inaccurately counting days with high amounts of non-wear time.⁵⁵ We will also assess engagement in other intervention components, including the percentage of action plans completed, which is objectively assessed via Qualtrics, with 100% indicating completion of all 19 action plans. Via self-report at 6 months, we will assess which of the 19 lessons were read and the frequency with which progress reports were reviewed, with options of *weekly*, *less than 1 time per week*, *less than 1 time per month*, and *never*.

Putative moderators will be assessed via self-report survey measures administered at baseline, including demographic (e.g., sex, age, education), psychosocial (e.g., stress,

self-efficacy), behavioral (e.g., pretreatment caloric intake and physical activity), and clinical (e.g., type 2 diabetes diagnosis) characteristics. A health literacy questionnaire, the Newest Vital Sign, will be administered orally by study staff at the baseline visit.⁵⁶

Table 3. Assessment Schedule in the Spark Trial.

Construct	Measure or assessment tool	Time Point (months)			
		0	1	3	6
Anthropometric, behavioral, and demographic measures					
Weight (primary outcome)	E-scale (Fitbit Aria Air) ⁴⁶⁻⁴⁸	•	•	•	•
Height	Self-reported ⁵⁷	•			
Caloric intake	ASA24 dietary recall (1 weekday, 1 weekend day) ⁴⁹	•			•
Diet quality	Healthy Eating Index, ⁵¹ measured by ASA24	•			
Physical activity	GLTEQ ⁴²⁻⁴³	•	•	•	•
Physical activity guideline adherence	Stanford Leisure-Time Activity Categorical Item (L-Cat) ⁵⁸	•		•	•
Step count ^a	Activity tracker (Fitbit Inspire 3)	•	•	•	•
History of self-monitoring	Self-reported use of self-monitoring of diet, steps, and weight in the month prior to study enrollment ⁵⁹	•			

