Sociodemographic and clinical characteristics	Self-reported age, race/ethnicity, sex, gender, sexual identity, birth country, marital status, education, employment, income, household size, # children in home, prediabetes, type II diabetes, hypertension, smoking	•			
Engagement metrics					
% days of self-monitoring (diet, steps, weight)	Digital tools (Fitbit app, Fitbit Inspire 3 activity tracker, Fitbit Aria Air e-scale, respectively)	•	•	•	•
% action plans completed	Action plans in Qualtrics	•	•	•	•
% lessons read	Self-reported frequency of reading weekly lessons				•
Progress reports viewed	Self-reported frequency of viewing weekly progress reports				•
Psychosocial measures					
Health-related quality of life	SF-36 ⁵⁴	•			•
Self-efficacy for dietary change	Weight Efficacy Lifestyle Questionnaire Short-Form (WEL-SF) ⁶⁰	•		•	•
Self-efficacy for exercise	Exercise Self-Efficacy Scale ⁶¹	•		•	•
Self-regulation for eating	Three Factor Eating Questionnaire (TFEQ-R18) ⁶²	•		•	•
Sleep	Pittsburgh Sleep Quality Index (PSQI) ⁶³	•		•	•
Motivation	Treatment Self-Regulation Questionnaire (TSRQ) ⁶⁴	•		•	•
Mastery for self-monitoring ^b	Self-Report Habit Index (SRHI) Automaticity subscale ⁶⁵⁻⁶⁶			•	

Construct	Measure or assessment tool	Time Point (months)			
		0	1	3	6
Self-efficacy for self-monitoring ^b	Adapted from Bandura's self-efficacy measure ⁶⁷ to assess self-efficacy for self-monitoring diet, steps, and weight	•	•		
Outcome expectations/realizations	Outcome Expectations ⁶⁸		•		•
Confidence in participating fully	Investigator-designed 1-item measure to capture confidence in participating in weight loss intervention over next 6 months		•		
Health literacy	Newest Vital Sign (NVS) ⁵⁶ via interview	•			
Weight bias internalization	Weight Bias Internalization Scale (WBIS) ⁶⁹	•			
Stress	Perceived Stress Scale (PSS-10) ⁷⁰	•			
Negative life events	Occurrence of negative life events over past 12 months	•			
Stages of change	Stages of change questionnaire in weight management (S-Weight) ⁷¹	•			
Social support	Social Support for Diet & Exercise ⁷²	•			

^aThis outcome will be collected only in the conditions that were asked to track steps (conditions 3, 4, 7, 8).

^bAt the 1-month assessment, these measures will be specific to what domain is being self-monitored (i.e., diet, steps, weight). Only participants in the conditions that are asked to track a given domain will be administered those measures.

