3.9.2 Quality Assurance

Participants enrolled in this study may not concurrently participate in other research studies where weight loss is targeted. In addition, participants will be asked to refrain from self-monitoring behaviors that are not assigned to them and refrain from using any other weight-related apps or activity trackers for the duration of the trial. In the first 2 weeks of the intervention, study staff will verify whether participants are self-monitoring correctly by checking their Fitbit data. If a deviation is found, staff will flag it in REDCap, and the participant will receive an automated email reminder indicating what they are supposed to self-monitor or not self-monitor. By explaining the rationale of the study prior to enrollment, we hope to minimize contamination between conditions. It is common practice for control group participants to still have their weights assessed for study evaluation purposes even if they are not instructed to weigh regularly. In a prior trial testing a daily self-weighing intervention, all participants received a scale at baseline, and control participants were instructed to use the scale only at the assessment time points⁷³; these procedures (which will be replicated here) were successfully enacted with no contamination found and negligible impact on outcomes.

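### Does it undermine the masked primary analysis that the study statistician also generated the allocation sequence?

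*Protocol*

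**What the plan says.** Three statements in the protocol bear on the point.

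- Section 3.4.2 (Baseline Visit and Randomization): "The allocation sequence was generated using SAS by the study's statistician". The sequence is stored in REDCap, stratified by sex assigned at birth, in permuted blocks of 8 for the 8 conditions.
- Section 3.9.1 (Masking): once data collection is complete, the study statistician "will analyze the primary outcome (weight change) in a masked fashion such that treatment assignment will not be revealed".
- Section 3.9.1 also says that "study staff will not have access to the allocation sequence". Participants and staff are openly unmasked to assignment.

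The protocol does not describe the analysis file, who prepares it, or when the codes are opened. Section 3.11 refers statistical analysis to a separate plan. Names are removed from the public text, so the shared role is visible but a shared person is not confirmed.

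**The concern.** The analyst is the only party the protocol describes as masked. If the analyst also wrote the list, and the access restriction is worded for study staff alone, a reader can fairly ask what keeps list and data apart. REDCap sharpens the question, because it holds the sequence and, under section 3.12, also serves data entry, randomization and participant tracking.

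There also seems to be a route to assignment that needs no list. The e-scale measures the primary outcome and is at the same time the tracking tool of one component. Those assigned to that component are "instructed to self-monitor their body weight daily via a Bluetooth enabled e-scale". For everyone else the protocol replicates an earlier trial in which "control participants were instructed to use the scale only at the assessment time points". Step counts, and some 1-month measures, exist only for participants assigned to that domain: "Only participants in the conditions that are asked to track a given domain will be administered those measures". An analyst with the full dataset could infer much of the assignment from which data are present.

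At stake is whether a report could claim a masked primary analysis that was not masked in practice. Analyst masking guards against analysis choices made with knowledge of which group is which.

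**Working it through.** The protocol gives no figure to reproduce. The check is whether the two tasks can coexist, and whether the data needed for the primary analysis reveal assignment.

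**1. What the list alone reveals.** I assume that each block of 8 contains each of the 8 conditions once, which is the natural reading of section 3.4.2. An analyst who holds the list and knows a participant's sex, but not the order of randomization, can say only that each condition has probability 1/8 over complete blocks. That is no information. With the order within the sex stratum, or an identifier that links to it, the condition can be read off exactly. Masking therefore depends on whether order or a linkable identifier reaches the analyst, and not on who wrote the list. No section says that either is supplied.

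**2. Whether the analysis can run without assignment.** Section 3.2 defines a main effect as the mean weight change over the four conditions with a component minus the mean over the four without it. If the three components carry neutral names and their levels neutral codes, swapping the two codes of a component reverses the sign of this difference and leaves its size unchanged. The comparison can be fitted and fixed before the code is opened. Section 3.9.1 already provides people who could prepare such a file, since staff are not masked to assignment.

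**3. Whether the outcome data reveal assignment.** Raw e-scale records would be telling.

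- Without the weight component: 4 assessments (0, 1, 3 and 6 months), and at each one participants weigh once and then "repeat it 2 more times for a total of 3 weight measurements per time point". That is 4 × 3 = 12 readings on 4 occasions.
- With it: weighing on up to 182 days, the period stated in section 3.8.2 for engagement.
- Step counts exist in conditions 3, 4, 7 and 8, so for 176 × 4/8 = 88 of the planned participants.

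These contrasts matter only if the data reach the analyst before the primary result is fixed. Section 3.9.1 claims masking for weight change alone. Section 3.8.1 builds that outcome from assessment weights, which participants also enter on a web check-in form, so daily records are not needed to compute it. Engagement, step counts and the domain-specific 1-month measures serve other analyses, for which no masking is claimed. No section gives the statistician the raw e-scale stream; section 3.9 names the retrieval software without assigning access to the analyst.

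**4. Side by side.** Section 3.4.2 records a task done in advance. Section 3.9.1 commits to a result later: assignment is not revealed to the analyst. The second commitment does not depend on the first task having been done by someone else.

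**The case for a change.** The strongest reply is that the protocol makes the masking commitment in its own section, so it should not rest on a document the reader cannot see. The two role descriptions match, the restriction on the list does not mention its author, and the protocol states no separate list-holder, recoded labels, limited REDCap rights or step for opening the code. Coded labels alone would not mask someone who also held the list together with the randomization order, or who worked from the full dataset. The remedy would be cheap: a sentence or two and one prepared file.

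Part of this stands. The same role does appear in both places, and the procedure is not spelled out in the protocol. Analyst masking also has some value in a trial where nobody else is masked. What does not stand is the step from unstated to unsecured. Section 3.9.1 commits to the outcome of the procedure, and the contents of an analysis file and the timing of code release are details that protocols commonly leave to the analysis plan. The data-driven route needs the further assumption that the analyst is handed records that the primary analysis does not use.

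**Conclusion.** No change follows. This is a gap in description that an analyst and a data manager would fill sensibly, and it contradicts nothing in the protocol. Its size is nil on every quantity that can be checked: no shift in the estimate, the power or the type I error is shown, and the primary outcome is a weight recorded by e-scale. Data collection has ended according to section 6, so a new sentence could act only on how the analysis file is prepared, and could not undo any earlier access to the list.

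The conclusion rests on two assumptions: that the primary analysis file carries assessment weights and coded components without randomization order or linkable identifiers, and that any file with daily weigh-ins or component-specific measures is opened to the analyst only after the primary result is fixed. Nothing in the protocol points the other way. A reader who wants reassurance can look in the analysis plan for who holds the code and when it is released. Stating this in section 3.9.1 would be a harmless clarification, but the validity of the trial's result does not depend on it.

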3.9.2 Quality Assurance

Participants enrolled in this study may not concurrently participate in other research studies where weight loss is targeted. In addition, participants will be asked to refrain from self-monitoring behaviors that are not assigned to them and refrain from using any other weight-related apps or activity trackers for the duration of the trial. In the first 2 weeks of the intervention, study staff will verify whether participants are self-monitoring correctly by checking their Fitbit data. If a deviation is found, staff will flag it in REDCap, and the participant will receive an automated email reminder indicating what they are supposed to self-monitor or not self-monitor. By explaining the rationale of the study prior to enrollment, we hope to minimize contamination between conditions. It is common practice for control group participants to still have their weights assessed for study evaluation purposes even if they are not instructed to weigh regularly. In a prior trial testing a daily self-weighing intervention, all participants received a scale at baseline, and control participants were instructed to use the scale only at the assessment time points⁷³; these procedures (which will be replicated here) were successfully enacted with no contamination found and negligible impact on outcomes.

3.9.3 Research Ethics Approval

The Stanford University Institutional Review Board (IRB) approved our study protocol on March 28, 2022. Protocol modifications will be communicated to all study investigators and approved by the IRB prior to implementation, and the trial registry will be updated accordingly.

3.9.4 Declaration of Interests

The investigators report no competing interests.

3.10 Sample Size and Statistical Power

See **Statistical Analysis Plan** for the Spark Trial in a separate document.

3.11 Statistical Analysis

See **Statistical Analysis Plan** for the Spark Trial in a separate document.

3.12 Data Management

REDCap will be used for direct data entry, randomization, and tracking participants' status in the study. REDCap is a secure, web-based software platform for building and managing data, with a particular emphasis on those from clinical research studies.

There is a version hosted at Stanford University. Data will be stored on Stanford Medicine Box, which is a secure, cloud-based document management platform.

3.13 Endpoint

The behavioral intervention is 6 months in length and will not be terminated early based on efficacy. The study is expected to end after we reach our target sample size and the final participant has completed the 6 month intervention and assessment.

4. Risks and Protection Against Risks

4.1 Potential Risks

Potential risks include: 1) breach of confidentiality; 2) psychological distress associated with answering questions about psychological or behavioral content (e.g., perceived stress level, weight bias, body weight) or engaging in the intervention; 3) medical risks associated with participating in a behavioral weight loss treatment. These risks are consistent with typical risks associated with research participation in behavioral weight loss studies and are expected to be minimal. There are no invasive procedures planned. We will monitor the occurrence of adverse events and serious adverse events as required for these types of intervention studies.

4.2 Safeguards to Minimize Risks

4.2.1 Participant Population and Screening

All participants will be adults with overweight/obesity who are otherwise healthy. Individuals who are pregnant or who have a medical condition that would limit participation in a behavioral weight loss intervention or be better suited for a more intensive or different type of intervention are excluded from our trial (e.g., individuals with a history of an eating disorder or cardiovascular event, uncontrolled diabetes mellitus or hypertension, cancer, dementia). Risks to participants are anticipated to be low given that we are examining evidence-based intervention strategies and promoting weight loss through lifestyle change (e.g., decrease intake of unhealthy foods, increase steps). We will not be including a vulnerable population (e.g., children, pregnant women) as participants.

To ensure participant safety in this study, a set of screening procedures that are common in behavioral weight loss interventions, such as ensuring participants are safe to engage in moderate intensity physical activity and ensuring participants do not have a medical condition that is contraindicated in a remote weight loss program will be employed.

4.2.2 Minimizing Risks

This study is expected to impose minimal risk for participants. The content of the weight loss intervention – including moderate-intensity physical activity and dietary change through reduction of unhealthy foods and increase of healthy foods – is commensurate with the current national guidelines for behavioral obesity treatment.

Communications about the study, confirmation of eligibility, and obtaining informed consent will be conducted via 1:1 phone or Zoom with a member of the study team (see ClinicalTrials.gov for the informed consent form). These communications will be conducted by a study staff member who is in a private room. Participants will be requested to complete these sessions in a private room when possible to protect their privacy. Only study team members will have access to the email account and telephone line used to communicate with participants. Participant data obtained during the study will be gathered by researchers who are HIPAA and CITI certified. Responses will be entered into a computer database that is password protected. Data will be stored on a remote server (not on a local hard drive) and will be encrypted and accessible only to select study investigators. Confidentiality will be enhanced by assigning a unique participant ID number to each participant. Identifying information will be removed from these datasets.

To minimize risks related to experiencing psychological discomfort, participants will be informed upfront of types of survey questions and assessment measures to expect, and will be made aware they can skip any questions they do not feel comfortable answering with no impact on their participation or compensation. Any participants, including those who experience discomfort as a result of completing intervention components, are able to discontinue participation from the study at any time. We expect minimal adverse psychological effects.

